9.4.5 Pregnancy Test

A serum pregnancy test will be performed on female subjects who are of childbearing potential during the screening visit (Visit 1) for both healthy volunteer donors and CF subject donors. For healthy volunteer donors, up to 2ml of blood will be obtained for this test. For CF subject donors, the serum pregnancy test is included as part of the screening visit procedures for the main study described earlier. A urine pregnancy test will be performed on female subjects of childbearing potential at Visit 2 for healthy volunteer donors and at Visit 1A for CF subject donors.

10 EVALUATIONS BY VISIT

In general, the order of the items listed below will be the chronological order in which they will be performed at each study visit. However, this order may change once the logistics are finalized for each visit prior to the start of the clinical trial.

For CF Subjects:

10.1 Visit 1 (Screening Visit: Day -42 to -10)

1. Review the study with the subject and obtain written informed consent and HIPAA authorization
2. Review the “Consent for Specimen Banking” and the “Consent for Collection and Use of your CFF Registry ID Number” and ensure that the subject has checked one of the two options (Subjects who elect not to provide specimens for the bio-repository or to provide their CFF Registry ID number are still eligible for this study)
3. Assign the subject a unique screening number
4. Perform and record RSSQ prior to any other study procedures
5. Record demographics and other baseline data
6. Record medical and surgical history, including a history of CF, genotype, diagnosis date, and CF signs and symptoms
7. Record concomitant medications
8. Review inclusion/exclusion criteria

9. Measure and record height and weight without shoes
10. Perform and record vital signs, including a blood pressure after the subject has been seated for 5 minutes
11. Perform and record oximetry
12. Perform a complete physical examination
13. Collect blood for clinical laboratory tests (comprehensive chemistry panel, ESR, hs-CRP, complete blood count with differential, direct bilirubin and LDH)
14. Collect urine for clinical laboratory test (urinalysis)
15. Collect blood for serum pregnancy test
16. Administer 3 puffs of albuterol 15 minutes prior to spirometry if subject is likely to require induction to obtain sputum at any visit
17. Perform and record spirometry
18. Schedule subject for ***Visit 2***
19. Screening procedures for optional diagnostic bone marrow aspiration, if applicable:
 - a. Ensure that the subject has checked one of the two options regarding this optional procedure on the consent form. (Subjects who elect not to complete this procedure are still eligible for this study.)
 - b. Review eligibility for bone marrow aspiration
 - c. Collect 10 ml blood for laboratory tests (infectious disease markers)
20. Record any AEs that may have occurred during the study visit from the time of consent

10.2 Visit 1A (if applicable, Optional Bone Marrow Aspiration) (Day -35 to -14)

1. Perform and record vital signs, including a blood pressure after the subject has been seated for 5 minutes
2. Review and record interval history
3. Review and record any changes to concomitant medications
4. Perform urine pregnancy test if applicable
5. Perform an abbreviated physical exam
6. Review inclusion/exclusion criteria
7. Perform bone marrow aspiration
8. Subject to rest for 30 minutes post-procedure
9. Record any AEs that may have occurred during the study visit

10.3 Follow-up Phone Call (if applicable, 24 (\pm 12) hours after Optional Bone Marrow Aspiration)

1. Review and record interval history
2. Review and record any changes to concomitant medications
3. Record any AEs that may have occurred since bone marrow aspiration

10.4 Visit 2 (Baseline Visit: Day 1)

1. Perform and record RSSQ prior to any other study procedures
2. Administer and review CFRSD prior to any other study procedures and record any AEs that occurred since Visit 1
3. Review and record interval history
4. Review and record any changes to concomitant medications
5. Review inclusion/exclusion criteria
6. Measure and record weight without shoes
7. Perform and record vital signs, including a blood pressure after the subject has been seated for 5 minutes
8. Perform and record oximetry
9. Collect blood for clinical laboratory tests (comprehensive chemistry panel, ESR, hs-CRP, complete blood count with differential, direct bilirubin and LDH) and vitamin D
10. Collect blood for inflammatory mediators (calprotectin, MPO, GM-CSF, IL-1 β , IL-6, IL-8, IL-17, and TNF- α)
11. Collect urine for clinical laboratory test (urinalysis)
12. Collect urine for pregnancy test prior to infusion
13. Administer 3 puffs of albuterol 15 minutes prior to spirometry if subject is likely to require induction to obtain sputum during the visit
14. Perform and record spirometry approximately 2 hours before hMSC infusion
15. Obtain sputum for clinical laboratory tests (quantitative culture and microbiology) and for research tests (cell count with differential, IL-1 β , IL-6, IL-8, IL-10, IL-17, GM-CSF, MIP-3 α , TNF- α , neutrophil elastase, α_1 -anti-trypsin, and MMP-9). Subjects will be asked to provide sputum via spontaneous expectoration. If a subject is unable to provide sputum spontaneously, then the subject may undergo sputum induction according to the current TDN SOP. Any AEs related to the sputum procedure will be recorded.
16. Temperature, blood pressure, heart rate, respiratory rate and oxygen-saturation are measured prior to the infusion. Subjects should be seated for 5 minutes prior to obtaining vital signs.
17. Perform a complete physical examination
18. Infusion of hMSCs
19. Temperature, blood pressure, heart rate, respiratory rate and oxygen-saturation are measured prior to infusion and at 10 (\pm 5), 20 (\pm 5), 30 (\pm 5), 60 (\pm 15), and 90 (\pm 15) minutes and 2 hours (\pm 15 minutes) and 4 hours (\pm 15 minutes) post-infusion completion and then every 4 (\pm 15 minutes) hours for the remainder of the 24-hour observation period. Subjects should be seated or lying down for 5 minutes prior to obtaining vital signs.
20. Administer 3 puffs of albuterol 15 minutes (\pm 15 minutes) after the completion of the hMSC infusion if subject is likely to require induction to obtain sputum during the visit
21. Perform and record spirometry 30 minutes and 4 hours (\pm 15 minutes) after the completion of the hMSC infusion

22. Monitor study participant for 24 hours (\pm 30 minutes) after completion of the infusion
23. Record any AEs that may have occurred during the study visit

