9.1.7 Spirometry

Spirometry will be performed at all study visits and in accordance with the current American Thoracic Society recommendations for the performance and interpretation of tests. Spirometry will be obtained approximately 2 hours prior to the start of the hMSC infusion and 30 minutes, 4 hours and 24 hours after completion of the infusion. Subjects will perform spirometry as is customary for that subject at clinical visits. If the subject typically does not take albuterol prior to spirometry, then he/she will not take albuterol prior to spirometry during the study. If the subject typically takes albuterol prior to spirometry, they he/she will take albuterol prior to spirometry for this study. However there is an exception. In any subject in which it is anticipated that he/she might not be able to produce sputum spontaneously at any one of the study visits in which sputum will be obtained, then those subjects will undergo sputum induction at all visits regardless of his or her ability to spontaneously expectorate sputum at the current study visit. In these cases, those individuals will receive three inhalations of albuterol sulfate via metered dose inhaler prior to all spirometric tests obtained during the study. Approximately 15 minutes after administering albuterol sulfate, pulmonary function testing will be performed. If a study subject is unable to produce sputum at the Baseline Visit (Day 1), then sputum will not be obtained at Visits 3 (Day 7) and 5 (Day 28).

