9.1.8 Acquisition of Sputum

Sputum (approximately 1.3-2.0 grams) will be obtained at Visit 2 (Day 1) prior to the infusion of stem cells and on Visits 3 (Day 7) and 5 (Day 28) via spontaneous expectoration. Sputum samples will be split according to priority for analyses. The first aliquot will be sent to the microbiology laboratory at University Hospitals Cleveland Medical Center where quantitative bacteriology will be performed, and the second aliquot will be processed and saved for research studies. Sputum will be processed according to the current standard operating procedure (SOP) developed by CF Foundation's Therapeutics Development Network. Subjects unable to spontaneously expectorate sputum will undergo sputum induction according to the current SOP developed by CF Foundation's Therapeutics Development Network. If a sputum sample cannot be produced, or the quantity of the sample is not sufficient for all the tests to be performed, this is not considered a deviation.

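### For subjects expected to need sputum induction, 9.1.7 calls for albuterol about 15 minutes before every spirometry, but the Day 1 list in 10.4 has no dose before the 4-hour test

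*Combined protocol and SAP*

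**What the plan says.** Section 9.1.7 sets the general rule. Subjects keep to their usual albuterol habit before spirometry, with one exception: anyone who might be unable to produce sputum spontaneously at a sputum visit. For that group, "those individuals will receive three inhalations of albuterol sulfate via metered dose inhaler prior to all spirometric tests obtained during the study". The next sentence fixes the interval: "Approximately 15 minutes after administering albuterol sulfate, pulmonary function testing will be performed". The same section schedules tests about 2 hours before the infusion and at 30 minutes, 4 hours and 24 hours after it.

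Section 10.4 gives the Day 1 steps:
- Item 13, for the pre-infusion test: "Administer 3 puffs of albuterol 15 minutes prior to spirometry if subject is likely to require induction to obtain sputum during the visit".
- Item 20: 3 puffs at 15 (±15) minutes "after the completion of the hMSC infusion if subject is likely to require induction to obtain sputum during the visit".
- Item 21: "Perform and record spirometry 30 minutes and 4 hours" (±15 minutes) after the infusion.

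No albuterol step precedes the 4-hour test. Section 10.5 item 10 gives the 24-hour test on Day 2 its own dose. Appendix II footnote d repeats the infusion-day spirometry times and windows but says nothing about albuterol.

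Spirometry change at 30 minutes, 4 hours and 24 hours is one of the safety measures listed under the primary endpoint (5.1). Section 15.3 summarizes pulmonary function at these times by patient and by dose cohort.

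**The concern.** The rule in 9.1.7 is sound: every test in an induction subject should be done at about the same time after albuterol, so that changes from baseline compare like with like. The Day 1 list breaks this at one time point. Item 20 reads as the complete post-infusion albuterol instruction, and nothing prompts staff to give another dose before the 4-hour test.

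If the list is followed, the 4-hour change from baseline in an induction subject compares a test done long after albuterol with one done shortly after it. A fall in FEV1 or FEF25-75 could then come from the infusion, from waning bronchodilation, or from both. With no control arm the data cannot tell these apart. Cohorts 1 to 3 have three subjects each (8.3.3), so a single induction subject is one third of such a cohort's 4-hour summary.

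**Working it through.** There is no planned figure to reproduce. The check compares the sections and subtracts dose time from test time.

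**Inputs**, in minutes after the end of the infusion:
- Item 20 dose (10.4): 15, window 0 to 30.
- 30-minute test (10.4 item 21; Appendix II footnote d): 30, window 15 to 45.
- 4-hour test (10.4 item 21; footnote d): 240, window 225 to 255.
- Required interval from dose to test (9.1.7): about 15.

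**Doses against tests on Day 1.** Tests: pre-infusion, 30-minute and 4-hour, so 3. Doses listed: items 13 and 20, so 2.

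**Interval = test time − dose time:**

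| Test | Dose listed | Nominal interval | 9.1.7 |
|---|---|---|---|
| Pre-infusion | Item 13 | 15 | about 15 |
| 30-minute | Item 20 | 30 − 15 = 15 | about 15 |
| 4-hour | None of its own; last dose is item 20 | 240 − 15 = 225 | about 15 |
| 24-hour | 10.5 item 10 | 15 | about 15 |

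For the 4-hour test the shortest interval is 225 − 30 = 195 minutes and the longest is 255 − 0 = 255 minutes. No use of the windows brings it near 15.

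**Does the added dose fit?** The 4-hour vital signs and the 4-hour spirometry share the window 225 to 255. Suppose vital signs are taken first, from 225. The dose can then be given from 225 up to 255 − 15 = 240. The test follows at 225 + 15 = 240 up to 240 + 15 = 255. All three steps stay inside the existing windows.

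**The case against.** The strongest reply is that 10.4 omits a step but does not contradict the rule. Section 9.1.7 covers all spirometric tests, and nothing in 10.4 forbids a dose before the 4-hour one. Section 10 is also not exhaustive on albuterol: subjects who habitually take it before spirometry have no line in any visit list, so staff must consult 9.1.7 anyway. This stands as a reason to expect that some or all staff would give the dose. It does not put the step in the list. Nor can one argue that the single item 20 dose is still prior to both tests, because the 15-minute sentence rules out a gap of 225 minutes. The remark opening section 10, that item order may change, cannot supply a missing dose.

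The second reply is that the harm is conditional. It needs staff to follow the list over 9.1.7, at least one induction subject, and a material change in albuterol effect over 225 minutes. The documents give neither the size nor the duration of that effect. This stands in full and limits the weight of the point.

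Three stronger readings are tempting, and the documents do not support them.
- *That the albuterol lines at Visits 4, 6 and 7 never apply.* They depend on induction being likely *during the visit*, and 9.1.8 places sputum only at Visit 2 Day 1, Visit 3 and Visit 5. But 9.1.7 also says that these subjects undergo induction at all visits, whether or not they can expectorate. Read literally, that triggers the lines; read with 9.1.8, it may mean sputum visits only. The wording is ambiguous, so a count of uncovered tests across the study would rest on one strict reading.
- *That the item 20 dose may come after the 30-minute test*, by pairing the latest dose (30) with the earliest test (15). That pairing would break both the order of items 20 and 21 and the rule in 9.1.7.
- *That dose escalation is at risk.* The DLT definition rests on graded infusion-related allergic toxicities in the first 24 hours, and the 3+3 rule counts DLTs. Neither uses a spirometric value.

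**Conclusion.** The inconsistency is real and confined to one step. For subjects designated for sputum induction, the list in 10.4 leaves the 4-hour spirometry without the albuterol dose that 9.1.7 requires. If the list is followed, that test falls about 225 minutes (195 to 255) after albuterol, against a nominal 15 minutes at baseline and at 30 minutes. The 4-hour change from baseline in FEV1 and FEF25-75 then mixes any infusion effect with any change in bronchodilator effect.

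The impact is minor. The spirometry summaries are descriptive, and the number of induction subjects is unknown, anywhere from 0 to 15. The size of any distortion cannot be computed from the documents. The conclusion assumes that staff work from the visit list; if they apply 9.1.7 directly, the problem does not arise. A correction is still worth making, because the measure is a listed one and the change is very small.

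**What to change.** In 10.4, for induction subjects, add a line giving 3 puffs of albuterol about 15 minutes before the 4-hour spirometry. Preferably give it after the 4-hour vital signs and oxygen saturation, within the existing ±15-minute windows: vital signs from 225 minutes, albuterol at 225 to 240, spirometry at 240 to 255. That order is a preference only. The documents describe no albuterol effect on vital signs, and the item 20 dose already falls among the earlier vital-sign checks.

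Reword item 20 so that its dose is timed about 15 minutes before the 30-minute test, not from the end of the infusion. The nominal time does not change.

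As an optional clarification, replace *during the visit* with *at any visit* in the albuterol lines for Day 2 and Visits 4, 6 and 7 (10.5, 10.8, 10.12 and 10.13). Section 10.1 item 16 already has that wording: "Administer 3 puffs of albuterol 15 minutes prior to spirometry if subject is likely to require induction to obtain sputum at any visit".

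The cost is one added line, one reworded line and, if the option is taken, a short wording change in four sections. For subjects, it is one more albuterol dose on Day 1, which 9.1.7 already requires. If vital signs are taken first, they and the spirometry use the early and late parts of their windows respectively.

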10.5 Visit 2 (Baseline Visit: Day 2)

1. Perform and record RSSQ prior to any other study procedures
2. Review and record interval history
3. Review and record any changes to concomitant medications
4. Measure and record weight without shoes
5. Perform and record vital signs, including a blood pressure after the subject has been seated or lying down for 5 minutes
6. Perform and record oximetry
7. Perform a complete physical examination
8. Collect blood for clinical laboratory tests (comprehensive chemistry panel, ESR, hs-CRP, complete blood count with differential, direct bilirubin and LDH)
9. Collect urine for clinical laboratory test (urinalysis)
10. Administer 3 puffs of albuterol 15 minutes prior to spirometry if subject is likely to require induction to obtain sputum during the visit
11. Perform and record spirometry 24 hours (\pm 1 hour) after the completion of the hMSC infusion
12. Schedule subject for ***Telephone Call Visit 1*** and for ***Visit 3***.
13. Record any AEs that may have occurred during the study visit

10.6 Telephone Call 1 (Day 4 or 5)

1. Review and record interval history since Visit 2
2. Perform and record RSSQ

10.7 Visit 3 (Day 7 \pm 2)

1. Review and record RSSQ prior to any other study procedures
2. Administer and review CFRSD prior to any other study procedures and record any AEs that occurred since Visit 2
3. Review and record interval history
4. Review and record any changes to concomitant medications
5. Measure and record weight without shoes
6. Perform and record vital signs, including a blood pressure after the subject has been seated for 5 minutes
7. Perform and record oximetry
8. Perform abbreviated physical examination

9. Collect blood for clinical laboratory tests (comprehensive chemistry panel, ESR, hs-CRP, complete blood count with differential, direct bilirubin and LDH)
10. Collect blood for inflammatory mediators (calprotectin, MPO, GM-CSF, IL-1 β , IL-6, IL-8, IL-17, and TNF- α)
11. Collect urine for clinical laboratory test (urinalysis)
12. Administer 3 puffs of albuterol 15 minutes prior to spirometry if subject is likely to require induction to obtain sputum during the visit
13. Perform and record spirometry
14. Obtain sputum for clinical laboratory tests (quantitative culture and microbiology) and for research tests (cell count with differential, IL-1 β , IL-6, IL-8, IL-10, IL-17, GM-CSF, MIP-3 α , TNF- α , neutrophil elastase, α_1 -anti-trypsin, and MMP-9). Subjects will be asked to provide sputum via spontaneous expectoration. If a subject is unable to provide sputum spontaneously, then the subject may undergo sputum induction according to the current TDN SOP. Any AEs related to the sputum procedure will be recorded
15. Schedule subject for ***Visit 4***
16. Record any AEs that may have occurred during the study visit

10.8 Visit 4 (Day 14 \pm 2)

1. Perform and record RSSQ prior to any other study procedures
2. Administer and review CFRSD prior to any other study procedures and record any AEs that occurred since Visit 3
3. Distribute CFRSD that the subject must complete between Visit 4 and Visit 5
4. Review and record interval history
5. Review and record any changes to concomitant medications
6. Measure and record weight without shoes
7. Perform and record vital signs, including a blood pressure after the subject has been seated for 5 minutes.
8. Perform and record oximetry
9. Perform abbreviated physical examination
10. Collect blood for clinical laboratory tests (comprehensive chemistry panel, ESR, hs-CRP, complete blood count with differential, direct bilirubin and LDH)
11. Collect urine for clinical laboratory test (urinalysis)
12. Administer 3 puffs of albuterol 15 minutes prior to spirometry if subject is likely to require induction to obtain sputum during the visit
13. Perform and record spirometry
14. Schedule Subject for ***Telephone Call 2*** and for ***Visit 5***
15. Record any AEs that may have occurred during the study visit

10.9 Telephone Call 2 (Day 21 ± 2)

1. Review and record interval history since Visit 4
2. Perform and record RSSQ
3. Review CFRSD and record any AEs that occurred since Visit 4

10.10 Visit 5 (Day 28 ± 2)

1. Review and record RSSQ prior to any other study procedures
2. Administer and review CFRSD prior to any other study procedures and record any AEs that occurred since Telephone call 2
3. Review and record interval history
4. Review and record any changes to concomitant medications
5. Measure and record weight without shoes
6. Perform and record vital signs, including a blood pressure after the subject has been seated for 5 minutes
7. Perform and record oximetry
8. Perform complete physical examination
9. Collect blood for clinical laboratory tests (comprehensive chemistry panel, ESR, hs-CRP, complete blood count with differential, direct bilirubin and LDH)
10. Collect blood for inflammatory mediators (calprotectin, MPO, GM-CSF, IL-1 β , IL-6, IL-8, IL-17, and TNF- α)
11. Collect urine for clinical laboratory test (urinalysis)
12. Collect urine for pregnancy test
13. Administer 3 puffs of albuterol 15 minutes prior to spirometry if subject is likely to require induction to obtain sputum during the visit
14. Perform and record spirometry
15. Obtain sputum for clinical laboratory tests (quantitative culture and microbiology) and for research tests (cell count with differential, IL-1 β , IL-6, IL-8, IL-10, IL-17, GM-CSF, MIP-3 α , TNF- α , neutrophil elastase, α_1 -anti-trypsin, and MMP-9). Subjects will be asked to provide sputum via spontaneous expectoration. If a subject is unable to provide sputum spontaneously, then the subject may undergo sputum induction according to the current TDN SOP. Any AEs related to the sputum procedure will be recorded
16. Schedule subject for **Telephone Call 3** and for **Visit 6**
17. Record any AEs that may have occurred during the study visit

10.11 Telephone Call 3 (Day 56 ± 2)

1. Review and record interval history since Visit 5
2. Perform and record RSSQ
3. Record any AEs that occurred since Visit 5

10.12 Visit 6 (Month 3 ± 14 days)

1. Perform and record RSSQ prior to any other study procedures
2. Review and record interval history
3. Review and record any changes to concomitant medications
4. Record any AEs that occurred since Telephone call 3
5. Measure and record weight without shoes
6. Perform and record vital signs, including a blood pressure after the subject has been seated for 5 minutes
7. Perform and record oximetry
8. Perform abbreviated physical examination
9. Collect blood for clinical laboratory tests (comprehensive chemistry panel, ESR, hs-CRP, complete blood count with differential, direct bilirubin and LDH)
10. Collect urine for clinical laboratory test (urinalysis)
11. Administer 3 puffs of albuterol 15 minutes prior to spirometry if subject is likely to require induction to obtain sputum during the visit
12. Perform and record spirometry
13. Schedule Subject for ***Visit 7***
14. Record any AEs that may have occurred during the study visit

